Official Title: Assessing the Safety of Nighttime Passy-Muir Valve Use and its Impact on Sleep Quality in the Long-Term Acute Care Hospital Setting: a Cross-Over Controlled Study

Clinical Trial Number: NCT06229639

Use date of study closeout: 9/1/2016

STUDY PROTOCOL AND STATISTICAL ANALYSIS PLAN

Study Protocol

Eligible participants were inpatients 18 years of age or older, who were admitted to Gaylord Specialty Healthcare following tracheostomy placement during an acute care hospital stay, were eligible for decannulation, and who had a tracheostomy tube size of six or smaller and did not require ventilation assistance. These patients were initially referred to the study by a Respiratory Care Practitioner (RCP). Patients also needed to meet all criteria outlined in Gaylord's decannulation protocol, along with the specific criteria required for the study. (**Table 1**). Eligible patients were then approached for study enrollment. Enrolled participants were given the FDA-approved PMV #2001 for the study. The PMV is a bias-closed, no-leak speaking valve that allows patients to speak at a level consistent with their normal vocalization range.

Participants were monitored and evaluated using the same outcomes and safety metrics typically used during the study site's decannulation protocol. This included an initial and daily evaluation by a Pulmonary or Critical Care Medicine consultant and daily morning arterial blood gas (ABG) measurements by an RCP. The RCP then conveyed ABG measurement to the covering therapists and Pulmonary or Critical Care Medicine consultants at shift change. The RCP then communicated daily with the covering Independent Medical Practitioner (IP). If participants failed to meet the decannulation or study criteria at any point during the protocol, then the IP was notified, and the protocol was to be canceled.

PMV Trial – Study Day One and Night One

On day one of the study period, participants were given a PMV to use during the day. If the PMV was tolerated without any acute vital changes (i.e., adverse reactions; **Table 2**), participants were instructed to keep the PMV on after 22:00, when it would typically be removed if still in place (**Figure 1**). Throughout the night, participants were kept on continuous telemetry for the duration of the study protocol. Nursing staff monitored and recorded heart rate, blood pressure, and temperature every four hours (e.g., 22:00, 02:00, and 06:00). The Respiratory Therapist (RT) on duty recorded oxygen saturation, end-tidal carbon dioxide (ETCO₂) levels via nasal cannula, and respiratory rate. Supplemental O₂ was given to participants as determined by the clinical opinion of the respiratory staff. Supplemental O₂ was noted if given to participants but not categorized as a serious adverse reaction requiring trial termination.

If at any time the participants experienced serious adverse reactions such as respiratory distress, stridor, or ETCO₂ greater than 60, PMV removal was scheduled (**Table 2**), and initiation of ventilatory support was planned. The trial would then be terminated and deemed unsuccessful. In the event of an unsuccessful PMV trial, the RCP would inform the IP and acquire ABG measurements. If this procedure did not improve the participant's respiratory condition, the next step would be to initiate ventilator support and request a chest X-ray.

Following night one, participants completed the Richards-Campbell Sleep Questionnaire (RCSQ) upon waking. The RCSQ is a six-question self-report questionnaire used to assess ICU patients' sleep quality.¹⁵ These six questions assess the domains of sleep depth, sleep latency, awakenings, ability to return to sleep, overall sleep quality, and overnight noise level.¹⁵ The responses were recorded on a 100 mm visual analog scale, with higher scores indicating better sleep levels than lower scores. The mean score represents the general perception of sleep quality, which was the secondary outcome of this study, evaluated by the sleep domain scores derived from the Richards-Campbell Sleep Questionnaire.

Tracheostomy Plug Trial – Day Two and Night Two

If study day one and night one were successful, the protocol was continued to day two. During day two, participants wore a tracheostomy cap, also known as a plug. If the plug was tolerated without any adverse response, participants were instructed to keep the tracheostomy plug in place throughout the night. Again, nursing staff monitored and recorded heart rate, blood pressure, and temperature every four hours, and the RT on duty recorded oxygen saturation, ET_{CO}₂ levels, and respiratory rate. Same as night one, if any adverse events or acute changes occurred, it was planned that the plug be removed, ventilator support would be started, and the trial considered a failure. If no adverse events occurred upon waking up following night two, the participants were again administered the RCSQ. Once completed, following night two, participants' roles in the study were done and continued with the decannulation protocol as appropriate.

Statistical Analysis

Continuous clinical and demographic characteristics were described with means and 95% confidence intervals, and categorical data were described with frequencies. Differences in categorical variables were evaluated using Fischer's exact test or Chi-Square testing as appropriate. Differences in continuous variables were analyzed using paired t-tests for normally distributed data and Wilcoxon signed-rank test for non-normally distributed data. Two-way ANOVA analysis and Tukey's multiple comparisons post-hoc test were used to analyze differences in continuous variables at three time points (22:00, 02:00, and 06:00). Complete case analysis was performed on the dataset, with only complete pairs of data from night one and night two at the three time points being included in the analysis. All data were analyzed via GraphPad Prism 9 (GraphPad Software, San Diego, CA). Statistical significance was defined as a p-value less than 0.05.

Criteria for Initiation of Decannulation Protocol and Other Study-Specific Criteria

Decannulation Criteria

Afebrile
Hemodynamically stable
Clear or stable chest x-ray
Controlled Secretions
Peak Cough Flow ≥ 160 L / m
Satisfactory on-going nutrition (low risk of aspiration)
No clinical evidence of tracheal obstruction
Ability to tolerate a speaking valve

Inclusion Criteria

Patient has evidence of respiratory insufficiency requiring a tracheostomy tube without current need for assisted ventilation.
Patient will be continuously monitored with telemetry.
Patient satisfies criteria for the delInitiationcannulation protocol and agrees to use the Passy Muir Valve during sleep.

Patient is able to follow directions following speech, language, and cognitive evaluations, or other screening completed during the Speech-Language Pathologist and physician assessment.

Patient is at least 18 years old.

An informed consent is signed by patient or Power of Attorney (POA).

Patient is able to tolerate the Passy Muir Valve during the day for a minimum of 6 continuous hours.

Patient has a maximum size #6 Shiley cuffless tracheostomy tube or equivalent.

Exclusion Criteria

Patient identified at time of admission as requiring invasive long-term assisted ventilation.

Patient with documented or suspected upper airway obstruction and/or surgery or permanent tracheostomy tube.

Patient is quadriplegic (due to the inability for a quadriplegic patient to manually self-remove the valve in case of emergency).

Patient or POA failed to sign consent.

Patient has a severe cognitive impairment as determined by a formal cognitive-linguistic evaluation by a licensed Speech Language Pathologist.

Patient unable to meet criteria for decannulation protocol or has failed decannulation protocol within last two weeks.

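### The only overnight analysis named compares means at three clock times in complete pairs, so it drops participants stopped on night one and is insensitive to brief or individual deterioration; no participant-level safety count is specified

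*Combined protocol and SAP*

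**What the plan says.** **Monitoring (PMV Trial – Study Day One and Night One).** Overnight, "participants were kept on continuous telemetry" throughout the study. Nursing staff "recorded heart rate, blood pressure, and temperature every four hours (e.g., 22:00, 02:00, and 06:00"). The respiratory therapist (RT) "recorded oxygen saturation, end-tidal carbon dioxide (ETCO₂) levels via nasal cannula, and respiratory rate"; no interval is given for these. The 22:00 reading falls at the start of overnight wear, because "participants were instructed to keep the PMV on after 22:00, when it would typically be removed if still in place".

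**Definition of harm (same section).** The stopping rule opens "If at any time the participants experienced serious adverse reactions such as respiratory distress, stridor, or ETCO₂ greater than 60". A participant who meets it has the trial ended and classed as unsuccessful. Supplemental O₂ is noted when given but does not end the trial.

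**Progression (Tracheostomy Plug Trial – Day Two and Night Two).** Day two follows only if day one and night one succeeded. An adverse event on night two makes that trial a failure.

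**Analysis (Statistical Analysis).** Two-way ANOVA with Tukey's test is used for "differences in continuous variables at three time points (22:00, 02:00, and 06:00"), on complete pairs from both nights. Paired t-tests or Wilcoxon signed-rank tests are listed for continuous variables, and frequencies with Fisher's exact or chi-square tests for categorical ones. In neither list is a safety variable named. The section mentions no count of failures, limit crossings or O₂ use, no worst value and no telemetry summary.

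**The concern.** Safety of nighttime valve use comes first in the study title, and sleep quality is labelled secondary. The protocol describes harm as something that happens to one participant at an unpredictable moment. The overnight analysis looks at something else: the average at three fixed times, in people with data from both nights.

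Two things follow. The participants most informative about valve safety, those stopped on night one, cannot appear in the comparison. And deterioration that does not trigger stopping, or that is treated with O₂, may fall between readings or be averaged away. A finding of no difference in ETCO₂, saturation or heart rate could then be read as reassurance that the analysis is not able to give.

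**Working it through.** **No figure to reproduce.** The documents state no sample size, SD, event rate or margin. Every n, SD and episode length below is an assumption.

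**Step 1. Who can enter the ANOVA.** Let N start night one and s be stopped that night. At most N − s reach night two, so at most N − s form complete pairs. The number of night-one stops in the ANOVA is 0 whatever s is. For example, with N = 20 and s = 2, the ANOVA has at most 18 participants, and the 2/20 = 10% who failed on the valve do not appear in it. The paired t-test and the Wilcoxon signed-rank test have the same limit, since each needs both nights.

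**Step 2. Brief episodes and fixed readings.** The window from 22:00 to 06:00 is 480 minutes. Take one episode of d minutes.
- Model A: the episode lies wholly inside the night with a random start. The chance that it spans 02:00 is d/(480 − d). The readings at 22:00 and 06:00 add essentially nothing.
- Model B: the start is uniform over the night and the episode may run past 06:00. The chance that it meets 02:00 or 06:00 is 2d/480.

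| d (min) | Model A | Model B |
|---|---|---|
| 5 | 5/475 = 1.1% | 2.1% |
| 15 | 15/465 = 3.2% | 6.3% |
| 30 | 30/450 = 6.7% | 12.5% |
| 60 | 60/420 = 14.3% | 25.0% |

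Simulation agreed with both formulas. The columns answer different questions and should not be mixed. They concern only the analysed times; the RT may have recorded more often.

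**Step 3. One participant in a mean.** If one of n participants is worse by D at a reading, the mean paired difference moves by D/n. With D = 20 units this is 20/10 = 2.0, 20/20 = 1.0 or 20/30 = 0.67. If D were ETCO₂, that participant would stay below the stopping limit only from a starting value of 40 or less.

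A larger D does not help the test. Suppose the other n − 1 differences are zero. The sample variance is (D² − D²/n)/(n − 1) = D²/n, the standard error is √(D²/n²) = D/n, and t = (D/n)/(D/n) = 1 for any D. The outlier inflates the SD as fast as it moves the mean.

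Simulated paired t-tests at one time point (a simpler stand-in for the ANOVA), with one participant raised by 20 units, gave p < 0.05 this often:

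| n | SD of differences 4 | SD of differences 6 |
|---|---|---|
| 10 | 1.5% | 3.5% |
| 20 | 3.3% | 4.4% |
| 30 | 4.0% | 4.8% |

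With nobody deteriorating, the rate was about 5%. One deterioration made a signal no more likely.

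**The case against.** The strongest reply is that the protocol already has a participant-level safety result. A stopping event at any time yields an unsuccessful trial, O₂ use is noted, and the plan provides frequencies and categorical tests with which both could be reported. This stands, and it limits the point in several ways.

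- A reader might infer that safety is to be judged on group means. The documents do not say so; the text defines no primary safety analysis.
- A reader might infer that individual deterioration would be nearly invisible. For stopping events that is too strong, because each is recorded as a failure. What is missing is any statement that failures will be counted and reported.
- A reader might picture a large ETCO₂ rise diluted in the mean. A rise that takes ETCO₂ above 60 triggers stopping. On night one, that participant leaves the ANOVA altogether. Exclusion is the problem for severe events, and dilution for lesser ones.
- A reader might infer that usable telemetry data are already held. The documents do not say that telemetry was stored or that it captured ETCO₂ or saturation. If the chart holds only the scheduled readings, a worst value after 22:00 is simply the worse of 02:00 and 06:00, and the chance of catching a brief episode does not improve.

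It is also fair to say that 22:00 is a reasonable reference. The valve was already worn and tolerated by day, so this is an on-device reading, and a morning arterial blood gas was taken as well. Neither fact brings participants stopped on night one back into a paired comparison.

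**Conclusion.** The point holds in this form: the one overnight analysis that the plan names does not match the protocol's own definition of harm, and no participant-level safety analysis is specified to fill the gap. The exclusion of night-one stops follows from the progression rule and the complete-pairs rule together and needs no numerical assumption. It tilts the overnight comparison towards those who tolerated both nights. The insensitivity to brief or lesser deterioration is illustrated, not measured: 1% to 14% detection at 02:00 for 5 to 60 minute episodes (Model A), and a mean shift of 2.0 to 0.67 units for n of 10 to 30.

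The documents do not show that any deterioration was missed or that failures went unreported. They show that the plan leaves this reporting to discretion. It should be corrected before the overnight comparison is used as evidence of safety.

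**What to change.** Specify as the main safety analysis, separately for each night and among all participants who started that night, the number and proportion with an exact confidence interval for:

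1. a stopping event or failed trial;
2. any recorded crossing of a protocol limit (those in Table 2);
3. supplemental O₂ use.

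State how many were enrolled and how many started each night. Present the two nights side by side, since night two contains only those who passed night one.

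Where the chart or RT record holds more than the scheduled readings, add each participant's worst recorded value after 22:00. Keep the three-time-point ANOVA as supportive, described as applying to participants who completed both nights.

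The cost is analysis-plan wording and some chart abstraction, with no new monitoring. The document gives a study closeout date of 9/1/2016, so the change should be labelled as a later addition. Intervals will be wide: with no events, the one-sided 95% upper bound is 1 − 0.05^(1/n), which is 25.9%, 13.9% and 9.5% for assumed n of 10, 20 and 30. Reporting that width shows how much safety information the sample can give.

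### The plan pairs its continuous comparisons but names only unpaired tests for categorical ones; between-night binary outcomes need McNemar, with night-one failures and oxygen use reported alongside

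*Combined protocol and SAP*

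**What the plan says.** **Tests.** The Statistical Analysis section pairs its continuous comparisons: "Differences in continuous variables were analyzed using paired t-tests for normally distributed data", with the Wilcoxon signed-rank test for non-normal data. For categorical variables it says: "Differences in categorical variables were evaluated using Fischer's exact test or Chi-Square testing as appropriate". No paired binary test is named. The same section allows categorical data to be summarised as frequencies.

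**Who reaches night two.** After a serious adverse reaction on night one, "The trial would then be terminated and deemed unsuccessful" (PMV Trial – Study Day One and Night One). The plug section opens: "If study day one and night one were successful, the protocol was continued to day two". The analysis is then restricted, with "only complete pairs of data from night one and night two at the three time points being included in the analysis".

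**Oxygen.** The night-one section says "Supplemental O₂ was given to participants as determined by the clinical opinion of the respiratory staff", and then "Supplemental O₂ was noted if given to participants but not categorized as a serious adverse reaction requiring trial termination". On night two "the RT on duty recorded oxygen saturation", along with ETCO2 and respiratory rate, but the oxygen sentences are not repeated. The Statistical Analysis section does not mention supplemental oxygen.

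**The concern.** The document describes a single group of participants, each seen on two consecutive nights. The natural use of a categorical test here is therefore a comparison between nights, and the two sets of observations are not independent. Fisher's exact and chi-square see only the two totals and ignore which participants had the event on both nights. Someone who needs oxygen on one night is more likely to need it on the next. With that positive correlation the unpaired tests overstate the variance of the difference. In a study whose title leads with safety, this error works against detecting a difference.

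Two related gaps affect how the safety results read. A participant who fails night one has no night two and so cannot be in the complete-pair set, and the plan names no denominator for failures. SpO2 is the variable that oxygen is given to change, so similar SpO2 on the two nights is not evidence of equal safety if it was reached with different oxygen use.

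**Working it through.** The documents state no sample size, event rate, SD, oxygen trigger or oxygen rate, so there is no figure of theirs to reproduce. Apart from the 0.05 threshold, every input below is assumed for illustration.

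**1. Variance.** Let p1 and p2 be the event proportions on the two nights, p11 the proportion with the event on both, and cov = p11 − p1·p2.
- Unpaired: [p1(1−p1) + p2(1−p2)]/n
- Paired: the same numerator minus 2·cov, over n

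Take n = 20, with 12 events on the PMV night and 6 on the plug night (p1 = 0.60, p2 = 0.30). Unpaired: (0.24 + 0.21)/20 = 0.0225, SE 0.150. If all six plug-night participants are among the twelve, cov = 0.30 − 0.18 = 0.12. Paired: (0.45 − 0.24)/20 = 0.0105, SE 0.102.

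**2. P-values for the same totals.** Fisher gives 0.111 and uncorrected chi-square 0.057 whatever the overlap. Exact McNemar is 2·P(X ≥ k), with X binomial on the discordant pairs, probability 0.5, and k the larger discordant count. Mid-p subtracts P(X = k). The correlation is cov/√(0.24 × 0.21).

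| Shared | Discordant | Correlation | Exact McNemar | Mid-p |
|---|---|---|---|---|
| 4 | 8 v 2 | 0.09 | 0.109 | 0.109 − 45/1024 = 0.065 |
| 5 | 7 v 1 | 0.31 | 0.070 | 0.070 − 8/256 = 0.039 |
| 6 | 6 v 0 | 0.53 | 0.031 | 0.031 − 1/64 = 0.016 |

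The paired difference is 30 points. Its 95% CI (Tango) is 9 to 52 with six shared and −11 to 62 with none shared.

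**3. False-positive rate.** Simulation with 20,000 replicates, n = 20, event rate 0.30 on both nights, nominal 0.05:
- correlation 0: Fisher 0.025, chi-square 0.053
- correlation 0.3: 0.007 and 0.021
- correlation 0.6: 0.0007 and 0.0036

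The unpaired tests become steadily more conservative.

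**4. Power of the replacement.** Suppose every plug-night user is also a PMV-night user, so all discordant pairs point one way. Exact McNemar then needs six of them (2 × 0.5⁵ = 0.0625; 2 × 0.5⁶ = 0.031). At n = 20 and 40% v 10%, P(Bin(20, 0.30) ≥ 6) = 0.58; at 30% v 10%, P(Bin(20, 0.20) ≥ 6) = 0.20. At n = 10 the figures are 0.05 and 0.006. Mid-p needs five (0.0625 − 0.0313 = 0.031), so at n = 20 P(X ≥ 5) is 0.76 and 0.37.

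**5. Night-one failures.** By the progression rule, every complete pair has a successful night one. An event that ended night one therefore counts zero on that night in the paired set, whatever the true rate. If 22 start and 2 fail, the pairs show 0/20 (Clopper-Pearson 95% CI 0 to 17%), while all starters show 2/22 = 9% (1 to 29%). If nobody failed, nothing changes.

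**6. Oxygen and SpO2.** To a first approximation, oxygen shifts the between-night mean difference by the difference in the share given oxygen times the SpO2 rise it produces. A difference of 10 to 30 percentage points and a rise of 2 to 4 points give 0.10 × 2 = 0.2 up to 0.30 × 4 = 1.2 points. The sign depends on which night had more oxygen. The shift is zero if use was equal on both nights, or if oxygen started only after the charted reading.

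**The case against.** The plan specifies no between-night binary endpoint, so the unpaired tests might never be used that way, and the words on appropriateness could be stretched to cover McNemar. The first part is fair. Even so, with one group and two nights no other main use is evident, and the section names paired tests explicitly where it intends them.

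A reader might infer that ignoring pairing distorts p-values in both directions, since 5/20 v 0/20 gives Fisher 0.047 but exact McNemar 0.063. That does not hold up. The reversal reflects the discreteness of exact McNemar; mid-p gives 0.031. For 12/20 v 6/20, McNemar rises well above Fisher only when few participants are shared (0.146 with three, 0.238 with none). Those cases imply correlations of −0.13 and −0.80, which are implausible for the same person on consecutive nights.

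A reader might also infer that failures and oxygen use go unreported. The documents do not say so. The frequencies sentence permits both to be reported, and a paired comparison cannot include someone without a second night. What stands is that no denominator is set.

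Nor do the documents show that oxygen hid desaturation, or favoured either device. They give no trigger, timing or rate. Participants had respiratory insufficiency, so some oxygen may have been ongoing and equal on both nights. SpO2 under usual discretionary oxygen is also a legitimate comparison of care as delivered, and SpO2 is not among the termination events given as examples in the text (respiratory distress, stridor, ETCO2 above 60).

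**Conclusion.** The point on tests stands: for between-night binary outcomes, Fisher's exact and chi-square rest on an independence assumption that this design breaks. Under positive within-patient correlation they are conservative, so a real safety difference could be missed. The size cannot be stated for this trial. In the assumed example the p-value moves from 0.11 (Fisher) to 0.031 (exact McNemar) at a correlation of 0.53, with little or no change near zero correlation.

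The other two parts are secondary. Night-one failures are structurally absent from the complete-pair set, which matters only if any occurred. Noted oxygen use has no stated role beside SpO2; the direction and size of any effect are unknown and may be zero. Tabulating oxygen would make the SpO2 result readable but would not separate device from oxygen, because the PMV night always came before the plug night.

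**What to change.** 1. For between-night binary outcomes (new or increased oxygen use, adverse reactions), replace Fisher's exact and chi-square with McNemar, exact or mid-p. State which, and lead with the paired risk difference and its 95% CI. Power will be low at small n, so a non-significant result should not be read as equivalence.
2. Report night-one failures over all participants who started night one, with an exact CI, separately from the paired analysis. Account likewise for any night-two failure dropped for missing time points.
3. Show oxygen use beside SpO2 at 22:00, 02:00 and 06:00 on each night, marked as new, increased or ongoing where the records allow. If night-two oxygen was not recorded, say so next to the SpO2 result. Note that oxygen use was discretionary and that night order was fixed.

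The document gives a study closeout date of 9/1/2016, so these are changes to analysis and reporting only. The cost is a record check and a short re-analysis of data largely already collected. The main risk is that night-two or baseline oxygen status was not recorded, in which case only the available information, or its absence, can be stated.

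### With one fixed order (PMV on night one, plug on night two), between-night RCSQ and vital-sign differences combine device and night, and the title's wording suggests more than the design supports

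*Combined protocol and SAP*

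**What the plan says.** The section PMV Trial – Study Day One and Night One assigns the PMV to everyone first: after a tolerated day, "participants were instructed to keep the PMV on after 22:00, when it would typically be removed if still in place". The RCSQ follows on waking, and its role is stated: "The mean score represents the general perception of sleep quality, which was the secondary outcome of this study".

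The section Tracheostomy Plug Trial – Day Two and Night Two then sets the order and the conditions for continuing:

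- Entry to the second day is conditional on the first: "If study day one and night one were successful, the protocol was continued to day two".
- The device then changes for all who continue: "During day two, participants wore a tracheostomy cap, also known as a plug".
- Overnight use in turn depends on how the daytime went: "If the plug was tolerated without any adverse response, participants were instructed to keep the tracheostomy plug in place throughout the night".
- The second questionnaire depends on the course of that night: "If no adverse events occurred upon waking up following night two, the participants were again administered the RCSQ".

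Participation ends after night two. The text describes no reversed sequence, no randomisation of order and no return to the PMV. Figure 1 is not available to the review, but the text gives only this order.

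The Statistical Analysis section prescribes paired t-tests or Wilcoxon signed-rank tests, a two-way ANOVA with Tukey comparisons over 22:00, 02:00 and 06:00, and a complete-case rule that keeps only pairs with data from both nights at those times. It has no period or sequence term and no caveat about order. The official title reads, in part, "Impact on Sleep Quality in the Long-Term Acute Care Hospital Setting: a Cross-Over Controlled Study".

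**The concern.** A within-person comparison removes stable differences between people. It does not remove anything that changes from the first night to the second. Between the two nights the participant gains another night of telemetry and four-hourly checks, and moves a day further along the decannulation pathway. Any effect of that on sleep or vital signs falls entirely on the plug side of every pair. It could create a difference or hide one, so a null result cannot be attributed to the devices either. A reader who takes the title at face value would do so.

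A second, separate matter is who is analysed. A pair exists only if night one succeeded, the plug was tolerated by day and readings were complete; the second RCSQ also required that night two passed without an adverse event. That is a selected group for comparing the nights. It would be the wrong group for describing how safely the PMV was worn on night one.

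**Working it through.** The documents give no sample size, SD or effect size, so there is no figure to reproduce. The check is whether the design can separate device from night.

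**Two nights.** Let μ be the PMV/night-one mean, D the effect of plug relative to PMV, and N the effect of night two relative to night one.

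| Observed cell | Intercept | Device | Night | Mean |
|---|---|---|---|---|
| PMV, night one | 1 | 0 | 0 | μ |
| Plug, night two | 1 | 1 | 1 | μ + D + N |

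The device and night columns are identical, so the rank is 2 for 3 parameters. The paired difference is (μ + D + N) − μ = D + N. Subject effects do not help: with 20 subjects (an arbitrary number) the rank is 21 for 22 parameters. For reference only, having both orders would give 22 of 22 if there were no carry-over.

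**Adding clock time.** The Statistical Analysis section does not name the two ANOVA factors; night/device and clock time are assumed here. The columns are intercept 1, device 1, night 1, clock time 2, device-by-time 2 and night-by-time 2, which makes 9. There are 2 × 3 = 6 distinct cells, and the rank is 6. With 22:00 as reference and k = 02:00 or 06:00:

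- Night one: μ, and μ + T_k.
- Night two: μ + D + N, and μ + D + N + T_k + (DT_k + NT_k).

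The six estimable quantities are μ, the two T_k, the sum D + N, and the two sums DT_k + NT_k. D, N, DT_k and NT_k are not estimable individually.

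**What this means for Tukey comparisons**, if all 6 × 5 / 2 = 15 pairs of cells are compared:

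- 3 pairs within night one involve only T_k.
- 3 pairs within night two involve T_k plus the aliased sums DT_k + NT_k. They describe night two correctly, but the trend cannot be assigned to the plug rather than to the night.
- 9 pairs between nights (3 at the same clock time, 6 at different times) contain D + N.

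**Safety denominator.** Suppose n participants begin night one and f fail it. Among starters the failure proportion is f/n. Continuation requires success on night one, so among complete pairs the count of night-one failures is 0 whatever f is.

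**Illustration only; every input is assumed.** Take D = 0, a two-sided paired t-test at 0.05, 10 to 30 pairs, and an SD of the paired RCSQ difference of 20 to 25 mm. The rejection probability is P(|t′| > t₀.₉₇₅), with t′ non-central t on n − 1 degrees of freedom and non-centrality N√n/SD. For n = 20, SD 20 and N = 5 mm, the non-centrality is 5 × √20 / 20 = 1.12 and the rejection rate is 18.6%. Over the whole range:

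| Assumed night effect | Rejection rate instead of 5% |
|---|---|
| 2 mm | 5.6% to 8.3% |
| 5 mm | 8.8% to 26.3% |
| 10 mm | 20.5% to 75.4% |

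The documents do not show which row applies, and the conclusion uses none of them.

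**The case against.** The case on the other side is substantial. The order follows the decannulation pathway. Each participant is compared with themselves, so the design can loosely be called a cross-over. The documents never claim randomised order or balanced periods. The Statistical Analysis section speaks only of differences; causal wording appears only in the title. No RCSQ hypothesis is written out. Sleep is secondary, and the study is closed ("Use date of study closeout: 9/1/2016"), so no reanalysis can separate the effects.

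Most of this stands, and it limits severity. It does not remove the point. Paired tests, pairs formed across the two nights and an RCSQ after each night leave no other evident paired RCSQ comparison. The title joins a causal noun to a claim of control, and nothing in the analysis text qualifies it.

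A reader might infer four stronger things that the documents do not support:

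- *That the ANOVA is uninformative, or conversely that every within-night contrast is untouched.* Each night's clock-time contrasts are valid descriptions of that night. A night-two trend, or a difference in trends, is not attributable to the plug.
- *That night-one failures were left out of the safety results.* No text says so. The complete-case rule is worded for the dataset as a whole but refers to between-night pairs at three time points. The bias arises only if it is applied to safety.
- *That lacking an RCSQ after a night with neither device contradicts the aim.* Usual removal at 22:00 is mentioned but never named as the comparator, so this is a limit on interpretation.
- *That the false-positive rate is inflated by a known amount.* The rates above rest wholly on assumed inputs.

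**Conclusion.** The point holds. In every between-night contrast, device and night are exactly aliased (rank 2 of 3; 6 of 9 with clock time) at any sample size. This follows from the single order in the text, and for the ANOVA from taking its factors to be night/device and clock time. A between-night difference in RCSQ or vital signs, or its absence, is a statement about PMV-on-night-one against plug-on-night-two and cannot be read as an effect of the PMV on sleep.

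A descriptive account of safety and tolerance on night one does not depend on order and is unaffected, provided that it covers everyone who began that night. Severity is minor to moderate: it concerns interpretation of the secondary outcome and of between-night vital signs.

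**What to change.** 1. In the title or design description, and in the Statistical Analysis section, describe the study along these lines: *a fixed-sequence, non-randomised comparison of PMV (night one) and plug (night two) among participants with complete paired data from both nights, which requires having passed night one and tolerated the plug by day; device and night effects cannot be separated.* Report between-night RCSQ and vital-sign differences, or their absence, as device and night combined.
2. State that the complete-pair rule applies only to the between-night comparisons. Report night-one safety and tolerance for everyone who began night one.

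The cost is rewording plus one table from records already collected, and more modest claims. No new data and no change of device order are requested. Naming the two ANOVA factors would help the reader, and a repeat study could add an RCSQ after a night with neither device, but neither is part of the required fix. The extra night would still leave device confounded with night (rank 3 of 5).
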